4.2 Scientific basis for the study design

Currently, there is no specific antiviral therapy for coronavirus infections. Few treatment studies have been conducted because most strains of human coronavirus cause self-limiting diseases and care is of a supportive nature. After the severe acute respiratory syndrome (SARS), the coronavirus was identified in 2002 and caused a major global outbreak, there has been a growing interest in the development of specific therapeutic agents. Since the SARS outbreak, new therapeutic agents which target the entry of viral proteins, proteases, polymerases and methyltransferases have been tested, however, none of them have been shown

to be effective in clinical trials. Thus, in the absence of a known effective therapy, the situation of a global public health emergency and evidence regarding the potential chloroquine inhibitor (CQ) in most coronaviruses, including SARS-CoV1 and others of a clinical nature, we intend to investigate the efficacy and the safety of CQ diphosphate in the treatment of hospitalized patients with severe respiratory syndrome due to SARS-CoV2. Preliminary trials of CQ repositioning in the treatment of COVID-19 have been encouraging.

This study uses an adaptable design that assesses a safe and effective therapeutic agent (chloroquine) for COVID-19 during the pandemic. The research product (chloroquine diphosphate) is easy to obtain, since it is produced on a large scale within the national territory and is widely distributed to all states by the National Malaria Program, of the Brazilian Ministry of Health. In addition, as the cases have increased, the low cost of chloroquine diphosphate and the free distribution by SUS is a great benefit. Randomization and blinding are essential to establish the effectiveness of chloroquine. In addition, by collecting clinical and virological data from enrolled patients using a standardized timeline and appropriate data collection instruments, we will also be able to provide valuable information about the clinical course and morbidities associated with severe COVID-19 in a diverse group of adult patients.

4.3 Placebo justification

The placebo will be used in this study as a mechanism for blinding participants, doctors and other professionals in the study.

5. STUDY POPULATION

5.1 Sample calculation

The sample for the primary outcome (reduction in lethality in patients with severe respiratory virus treated with a high dosage of chloroquine compared to a low dosage) was calculated based on the following assumptions:

- 1. The 20% lethality incidence in critically ill patients per year in the low dosage group;
- 2. High dosage chloroquine will be able to reduce lethality by at least 50% compared to low dosage chloroquine;

Thus, considering a test of differences in proportions between 2 groups of the same size, with power of 80% and alpha of 5%, 394 participants will be needed (197 per group). Considering 10% losses, the sample size is 440 participants.

5.2 Inclusion criteria

- 1. Adult aged 18 years or older, at the time of inclusion (children under 18 will not be included due to the recognized lower lethality in previous published studies, and the difficulty of consent in the context of a public health emergency);
- 2. Hospitalized;
- 3. And presents with clinical suspicion of COVID-19 AND:
- Respiratory rate > 24 bpm AND/OR
- Heart rate > 125 bpm (in the absence of fever) AND/OR
- Peripheral oxygen saturation <90% in ambient air AND/OR
- Shock (defined as MAP <65 mmHg, requiring a vasopressor or oliguria or lowering the level of consciousness)

5.3 Exclusion of specific populations

Children and adolescents will be excluded.

5.4 Inclusion of vulnerable participants

N/A.

5.5 Recruitment and retention strategies

5.5.1 Recruitment

It is expected that patients with COVID-19 will come to the HPSDRAA, in the northern zone of Manaus, a referral hospital for hospitalization of serious cases of the new virus, as provided for in the contingency plan to confront Covid-19 in Amazonas. Therefore, no further efforts are needed to recruit potential subjects. Recruitment efforts may, however, include the dissemination of information about this study to medical professionals and health staff at the hospital.

Patients with respiratory syndrome will be assessed for eligibility. The screening will begin with a brief discussion with the study team. Information about the study will be presented to potential subjects (or legally authorized representatives) and questions will be asked to determine possible eligibility.

As an additional recruitment strategy, centers included will be:

- Hospital Santa Júlia, Manaus-AM
- Fundação Municipal de Saúde, Niterói-RJ
- Hospital Universitário Maria Aparecida Pedrossian, Campo Grande-MS
- Hospital Regional de Mato Grosso do Sul, Campo Grande-MS

5.5.2 Retention

Not applicable, as all follow-up takes place during the patient's hospitalization period and the outcomes are discharge or death.

5.5.3 Compensation plan for subjects

There will be no financial compensation. All assistance will be provided free of charge by the institutions, part of the Unified Health System (SUS).

5.5.4 Costs

There is no additional cost for the research subjects, nor for the institution, and the procedures to be evaluated will be performed according to the routine and individual medical indication.

6. STUDY DRUG

6.1 Description of the study drug

Chloroquine is indicated for the prophylaxis and treatment of acute cases of malaria caused by *Plasmodium vivax*, *P. ovale* and *P. malariae*. It is also indicated for the treatment of hepatic amebiasis and, together with other drugs, it has clinical efficacy in rheumatoid arthritis, systemic lupus erythematosus and discoid lupus, sarcoidosis and photosensitivity diseases such as *porphyria cutanea tarda* and severe polymorphic eruptions triggered by light (https://www.far.fiocruz.br/wp-content/uploads/2017/02/Cloroquina-ProfSaude.pdf).

Chloroquine binds moderately (60%) to plasma proteins and undergoes considerable biotransformation through the hepatic cytochrome P450 system into active metabolites, desethylchloroquine and bidesethylchloroquine. These metabolites can reach plasma concentrations of 40 to 10% of the chloroquine concentration, respectively. The chloroquine S (+) enantiomer has both greater binding to plasma proteins and greater metabolic clearance than the R (+) enantiomer. The 4-aminoquinolines derivatives bind to nucleoproteins and interfere with protein synthesis; inhibit DNA and RNA polymerase. They concentrate on the parasite's digestive vacuoles, increasing the pH, interfering with the parasite's ability to metabolize and use red blood cell hemoglobin.

Chloroquine is well-absorbed in the gastrointestinal tract. Drug distribution is relatively slow in an apparently very large volume (>100 L/kg). Chloroquine binds moderately (60%) to plasma proteins and undergoes considerable biotransformation through liver CYP enzymes. Renal chloroquine clearance accounts for about half of its total systemic clearance.

Although the drug ideally has an injectable presentation in some countries, for this type of use in critically ill patients, it is not available in Brazil and in most countries.

Chloroquine exhibits complex pharmacokinetics in adults and children, so that plasma levels of the drug shortly after its administration are determined by the rate of distribution and not by the rate of elimination. Due to the extensive connection with the tissues, a loading dose

is necessary to obtain effective plasma concentrations. Chloroquine's half-life increases from (72 to 120) hours, as plasma levels decline. The terminal half-life varies from (30 to 60) days and traces of the drug may be found in the urine for years after therapeutic use. In addition to its antiparasitic effect, chloroquine has antipyretic and anti-inflammatory action. It presents fast and almost complete absorption; with plasma peak in (1 to 2) hours; It is widely distributed in tissues, concentrating on the iris, choroid and less on the cornea, retina, sclera and also on red blood cells. Chloroquine crosses the placenta and is distributed in breast milk. Plasma half-life of (72 to 120) hours; metabolized in the liver and excreted slowly in the urine. The chloroquine (chloroquine diphosphate) produced by Farmanguinhos is available in the form of a white circular, flat, grooved tablet.

6.2 Dosage and administration

Below is a description of the dosages for the groups in this study:

| Group 1 (high | her dose – 10 days) | |
|-------------------------|---|---|
| | 1st daily dose | 2 nd daily dose |
| D1 – D10 | 4 tablets of 150mg (600mg) | 4 tablets of 150mg (600mg) |
| Group 2 (low | er dose – 5 days CQ + 5 days placeb | 00) |
| D1 (Loading dose) | 3 tablets of 150mg (450mg) + 1 tablet of placebo | 3 tablets of 150mg (450mg) + 1 tablet of placebo |
| D2 – D5 | 3 tablets of 150mg + 1 tablets of placebo | 4 tablets of placebo |
| D6 – D10 | 4 tablets of placebo | 4 tablets of placebo |

The medication will be administered via oral administration (or via nasogastric tube in case of orotracheal intubation - OTI). All treatment medications will be provided by Farmanguinhos.

6.3 Dose escalation

Not applicable, as this would greatly increase the sample size, not allowing conclusions in time for its use in the current public emergency situation.

6.4 Dosage modifications and concomitant drugs

To be judged by the results that will be portrayed in the literature, in real time, the study's monitoring committee may decide to change the dosage used in the study, as well as the possibility of adding other concomitant drugs.

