1.11.2 Safety

Given the severity of the disease COVID-19, there is no study pre-specifying criteria for interrupting follow-up. The protocol team will review blind AE/SAE data every 2 weeks. If there is a worrying number of unexpected AEs, the researcher will request a review of the non-hidden security data in an ad hoc meeting with the external security monitoring committee, which should take place in real time, via videoconference.

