7. MEASURES TO MINIMIZE BIAS: RANDOMIZATION AND BLINDING

An electronically generated randomization list was prepared by an independent statistician, with 110 blocks of 4 participants per block. This randomization list was generated on R software (Package 'blockrand'). The list will be accessible only to non-blinded pharmacists in the study, in an attempt to minimize observation bias. Participants will be randomized by the study pharmacist to their designated treatment regimen at the time of inclusion and will be subsequently identified throughout the study only by their allocated study number, always assigned following chronological order. In case of SAEs, unmasking will be available to DSMB members, and preliminary analyses will be performed even before the scheduled interim analyses, in order to guide early halting of any of the CQ arms. The randomization and blinding procedure will be described in a specific SOP.

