| | | 21 | 0.3 | 0.638 | 2.8 | |
| 50% | 5 | 5 | 6 | 2 | | 0.0024 |
| | | 32 | 1.1 | 0.882 | 2.4 | |
| 75% | 2 | 9 | 1 | 4 | | 0.0074 |
| | | 42 | 2.0 | 0.978 | 2.0 | |
| 100% | 9 | 1 | 0 | 1 | | 0.0220 |

The procedure will be based on the calculation of the Z value of the difference of proportions test in each of the analyses, and the study will continue if this value is between the values of the lower and upper limits and will be interrupted if it is above the upper limit (by rejection H0) or below the lower limit (for futility), remembering that the latter can be ignored without prejudice to the calculations.

All calculations in this report were made in the R environment, version 3.6.1, with the functions implemented in the TrialSize and gsDesign packages. Other intermediary analyzes can be carried out throughout the study to periodically monitor the safety of participants and will provide possible prior information on treatment to the DSMB and Ministry of Health.

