11.9 Data publishing and sharing policy

To avoid premature release of data, this protocol specifies that the efficacy data for a study that has not yet been completed due to insufficient enrollment should not be published.

An independent monitoring committee will review the results of an interim analysis of study data to make recommendations on whether the study should continue or not.

It is important to note that investigators will remain blind to any analysis results; study data will only be released if the trial is interrupted based on a recommendation from the monitoring committee or has reached its target number of outcomes or amount of follow-up from participants.

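### Section 6.4 lets a monitoring committee decide literature-driven dosage changes, although every monitoring body whose data access is described sees unblinded or interim results; a team without by-arm results should decide.

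*Protocol*

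**What the plan says.** Section 6.4 makes changes to the regimens depend on the emerging literature and provides that the study's "monitoring committee may decide to change the dosage used in the study". The same sentence covers adding concomitant drugs.

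Other sections describe what the monitoring bodies see and do:

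- Section 1.11.2: a worrying number of unexpected adverse events leads to "review of the non-hidden security data in an ad hoc meeting with the external security monitoring committee". Routine review is different: "The protocol team will review blind AE/SAE data every 2 weeks".
- Section 7: "In case of SAEs, unmasking will be available to DSMB members, and preliminary analyses will be performed even before the scheduled interim analyses". The stated purpose is to guide early halting of either arm.
- Section 10.2: further intermediate analyses for safety are allowed, and these "will provide possible prior information on treatment to the DSMB and Ministry of Health".
- Section 11.9: the monitoring body there, described as independent, "will review the results of an interim analysis of study data to make recommendations on whether the study should continue or not". On the investigators, the same section says: "It is important to note that investigators will remain blind to any analysis results".
- Section 11.11: amendments are written, signed by the investigator and approved by the national ethics commission (CONEP) before use, except for priority safety reasons.

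**The concern.** The primary objective compares two dosages. Whoever can change a dosage can change what the trial tests. Section 6.4 names published results as the trigger, but whether and how to act on a publication is a matter of judgement. If those judging know the deaths by arm, nobody can show afterwards that this knowledge played no part.

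A second problem is leakage. A change of regimen announced by a body known to have seen by-arm results invites blinded investigators to guess which way those results point.

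An analysis plan can settle which patients are compared. It cannot alter who decides the dosage, so the matter belongs in the protocol.

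**Working it through.** **1. The plan's own figures.** With 20% against 10% deaths, two-sided 5% and 80% power, n per group = (1.960 + 0.842)² × (0.20×0.80 + 0.10×0.90) / 0.10² = 196.2, so 197 per group and 394 in all, as stated. Adding losses, 394/0.9 = 438, close to the stated 440. The one-tailed p limits in 10.2 (0.0008, 0.0024, 0.0074, 0.0220) give Z = 3.16, 2.82, 2.44, 2.01. The lower limits at the three interim looks are −0.59, 0.36 and 1.11. None of these figures is in dispute.

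**2. Who sees what.**

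| Body as named | Section | Described access |
|---|---|---|
| The study's monitoring committee | 6.4 | not described |
| External security monitoring committee | 1.11.2 | unblinded safety data |
| DSMB | 7 | unmasking after SAEs, unscheduled analyses |
| Independent monitoring committee | 11.9 | interim results |
| Protocol team | 1.11.2 | blinded AE/SAE data |
| Investigators | 11.9 | blind to analysis results |

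The protocol does not say that the first four rows are one body. It describes no monitoring committee that is blinded.

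**3. How informative an interim result is.** Let t be the information fraction. The chance of passing 2.01 at the end if the current trend continues is CP = 1 − Φ[(2.01 − Z/√t)/√(1−t)]. At the lower and upper ends of the continue zone it is 0.01% and nearly 100% (t = 0.25), 1.7% and 99.7% (t = 0.50), and about 7% and 95% (t = 0.75).

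These are the extremes. CP lies between 10% and 90% when Z is between √t × (2.01 − 1.28√(1−t)) and √t × (2.01 + 1.28√(1−t)). The share of continue-zone results in that range, under equal mortality and taking each look separately, is:

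- 25% look: Z from 0.45 to 1.56; 0.267/0.722 = 37%
- 50% look: Z from 0.78 to 2.06; 0.198/0.357 = 55%
- 75% look: Z from 1.19 to 2.30; 0.107/0.126 = 85%

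So the committee always knows the direction and strength of the trend, but it often does not know how the trial will end.

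**4. Type 1 error.** The inputs are the limits in step 1, equal mortality at every dosage, normal increments and looks at 25/50/75/100%, simulated over 6 million paths. The post-change statistic is (B(1) − B(t))/√(1−t), with B(t) = Z√t, tested once at the end against 2.01. Someone who knows Z does better with post-change patients only when Z < 2.01 × (1 − √(1−t))/√t, which is 0.54, 0.83 and 1.16 at the three looks. One-sided false-positive rates:

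| Rule | Change at 25% | At 50% | At 75% |
|---|---|---|---|
| All patients, fixed in advance; futility ignored | 2.5% | 2.5% | 2.5% |
| All or post-change, chosen knowing Z; futility ignored | 3.5% | 4.0% | 4.3% |
| Same choice; futility always followed (planned 2.3%) | 2.9% | 2.5% | 2.3% |
| Post-change only, chosen without knowing Z; futility ignored | 2.3% | 2.5% | 3.1% |

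If a pre-change-only comparison tested at 2.01 is also open, the rate is 5.1% to 5.3% with futility ignored and 3.1% to 4.5% with it followed. Ignoring futility is permitted by 10.2.

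**The case against.** The strongest case against has four parts.

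- **Identity.** That the committee in 6.4 is unblinded is an inference across several names in a translated text. This stands as a limit on the claim. It does not remove it, because no blinded committee is described, and if one is meant, 6.4 should say so.
- **Safeguards.** The trigger is public and can be checked, and 11.11 requires a signature from a blinded investigator as well as ethics approval. These make the change traceable. They do not blind the people who choose it.
- **Safety.** In a trial without pre-specified stopping rules (8.1.2), one may prefer that those who know toxicity by arm decide on dosage. That is a fair argument for their power to halt an arm, which section 7 already gives. It is weaker for changes prompted by publications.
- **Size.** A reader might infer that 6.4 in itself inflates type 1 error. The documents do not support that: they let the committee change the dosage, and nothing lets it choose which patients are compared. Even a blinded choice of post-change patients can exceed 2.5% (3.1% at the 75% look), so fixing the comparison matters as much as who decides.

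A reader might also infer that the committee would practically know the final result. Step 3 shows that this is not so in general, least of all at the 75% look.

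**Conclusion.** The point holds in a limited form. Section 6.4 places a decision over the compared regimens with a committee that, on everything the protocol describes, is likely to have seen results by arm. What is lost is demonstrable independence from the trial's own deaths, together with some protection of the investigators' blinding. Both losses arise only if the power is used, but they could not be repaired afterwards.

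No error inflation follows of necessity. The 3.5% to 4.3% range assumes equal mortality at all dosages, a choice between all and post-change patients made with knowledge of Z, and a futility limit that is ignored. The documents do not show that such a choice would be made.

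Nor do they support reading 6.4 as contradicting 6.3 or 11.11, or as undermining the sample size of 394 or 440. This is a cheap improvement in governance and not an error in the calculations.

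**What to change.** Reword 6.4 along these lines:

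> A change of dosage, or the addition of concomitant drugs, prompted by published results is decided by the protocol team without access to any results by arm. It is made by amendment under 11.11 that cites the published evidence and fixes which participants enter the primary comparison. The monitoring committee may state only whether it has a safety objection. Its powers to recommend stopping and to guide halting of an arm (7, 11.3, 11.9) are unchanged.

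The words on access to results are needed because 1.11.2 documents the protocol team's blinding only for AE/SAE data, and 8.1.2 has that team and the safety committee supervising together with frequent analyses.

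The cost is a few sentences and no extra patients. The committee loses direct power over literature-driven changes, and a safety objection to a proposed change may cost some days. Such an objection, or its absence, can still carry limited information about results by arm, so the fix reduces the leakage without removing it.

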6.5 Acquisition

Therapeutic agents will be sent by Farmanguinhos to the referral hospitals.

6.6 Preparation, handling, storage and responsibilities

After the inclusion of the participants with suspected COVID-19, who are hospitalized in the participating hospital, the participants will receive a prescription for Chloroquine/Placebo and will be referred to the study pharmacist who will be responsible for randomization in the treatment group and allocation of study medications (methodology best described posteriorly).

All test drugs (chloroquine and placebo), will be from the same batch, stored in their original packaging in the hospital's clinical pharmacy sector. Chloroquine diphosphate/placebo tablets will be suitable for unit dose dispensing for each participant during the treatment period. A label with the study reference, patient number (to be filled in) and the information "Product for use in clinical studies" will be attached to each blister/package.

The investigational products will be stored in accordance with the manufacturer's recommendations, inside the original packaging and in places with restricted access; and in accordance with Good Drug Storage Practices, as defined by law.

The investigator or other team member with permission to store and distribute the experimental product is responsible for ensuring that the experimental product used in the clinical study is kept safe and in compliance with applicable regulatory requirements. Every experimental product must be distributed according to the randomization list and by the study

pharmacist to ensure that an accurate record of the distributed and returned experimental product is maintained. A record of all study medication will be kept in the investigator's file.

Data regarding the date of receipt, the batch number, the expiration date and the date of use will be recorded for each of the study medications. An experimental drug registration diary will be kept at the study clinic. Any question related to the quality perceived at the time of receipt or during the use of an experimental product (deficiency of the investigational product in terms of condition, appearance, relevant documentation, labeling, expiration date, etc.) must be notified immediately. Under no circumstances should the investigator supply the experimental product to third parties, allow the experimental product to be used for purposes other than those indicated by this clinical study protocol, or discard the experimental product in any other way.

